**Table 4.1 Dosing Guidelines**

Cohort	Total Daily Dose a	Dose per Administration	Number of Subjects
Dose Escalation Cohorts: Part 1			
	25 mg	1 cap x 25 mg x twice a week	3-6 b
1 a	25 mg	1 cap x 25 mg x qod	3-6 b
2	25 mg	1 cap x 25 mg x qd	3-6 b
3	50 mg	2 caps x 25 mg x qd	3-6 b
4	100 mg	1 caps x 100 mg x qd	3-6 b
5*	150 mg	2 caps x 25 mg & 1cap x 100 mg x qd	3-6 b
6	200 mg	2 caps x 100 mg x qd	3-6 b
7	250 mg	2 caps x 25 mg & 2 caps x 100 mg x qd	3-6 b
8	325 mg	1 cap x 25 mg & 3 caps x 100 mg x qd	3-6 b
9	425 mg	1 cap x 25 mg & 4 caps x 100 mg x qd	3-6 b
10	550 mg	2 caps x 25 mg & 5 caps x 100 mg x qd	3-6 b
Food-effect a	400 mg	4 caps x 100 mg qd	at least 6
Expanded Cohort: Part 2			
Expanded e	300 mg	3 caps x 100 mg x qd under fasting conditions	approx. 50-60

\*Starting from Cohort 5, the dose escalation will follow a modified Fibonacci scheme (increase by 50%,

30%, and 25%)

To avoid potential non-compliance due to capsule burden, the dose escalation may be stopped at the dose level of 550 mg/daily

[figure not shown]
aTotal daily dose must be administered one hour prior to or two hours after the meal [Exceptions: 1) Cohort 1 is dosed every other day and 2) Food-effect Cohort]

bIf a DLT is seen in one of three treated subjects, an additional three subjects will be treated at the same dose level

cBased on the safety profile and PK results of the Food-effect cohort, the dose of 300 mg qd under fasting conditions has been defined as MTD/RP2D and should be further evaluated in the Expanded Cohort

Preliminary PK results reported in subjects enrolled in Cohorts 1-3, have shown that ARQ 087 has a long half-life (~ 1 week) and accumulates with continuous dosing in human subjects (~4 to 14 fold across all cohorts, 4 to 8 fold in cohorts dosed at  $\geq 100$  mg qd). Additionally, preliminary PK results showed that Day 22 exposure (AUC and  $C_{max}$ ) remained essentially the same when increasing the dose from 250 to 425 mg qd, suggesting that drug exposure has reached a plateau at dose levels above 250 mg qd. The ArQule Medical Monitor and Investigator(s) will review all significant ARQ 087-related toxicities and PK data to determine if the dose escalation schedule requires modification. Intermediate doses or different drug administration schedules (e.g., 2 weeks on/1 week off) may be investigated after agreement between ArQule's Medical Monitor and the Investigator(s).

## 4.2 Rationale for Study Design

### 4.2.1 Part 1: Dose Escalation/Food-effect Cohorts

This is the FIH, open-label clinical study with ARQ 087. This study will be conducted to evaluate the safety, tolerability, pharmacodynamic, and pharmacokinetics of ARQ 087 in subjects with advanced solid tumors.

The principal objective of Phase 1 studies is the assessment of the safety, tolerability, pharmacokinetics, and pharmacodynamics as well as determination of the RP2D of a new drug. For traditional chemotherapeutic agents that show limited selectivity for cancer cells over normal cells, RP2D is generally set at the MTD. However, for targeted agents, such as ARQ 087, the RP2D range may be below the MTD. For such therapies, it is important to collect pharmacokinetic and pharmacodynamic data to establish the dosing regimen that achieves the desired plasma concentration required for the intended pharmacologic effect.

Although pharmacokinetic and pharmacodynamic results may ultimately lead to selection of a lower dose, it is considered important to establish the clinical toxicity, including DLT as part of a thorough clinical evaluation of anticancer drugs. Therefore, in the current study dosing may be escalated beyond what is expected to produce therapeutic levels.

#### 4.2.2 Part 2: Expanded Cohort

Once the MTD/RP2D is determined, subjects with advanced solid tumors with FGFR genetic alterations, including iCCA with FGFR2 gene fusion, will be enrolled in Part 2, the signal finding Expanded Cohort.

### 4.3 Selection of Initial Dose

Based on the findings from the 4-week toxicity studies, the rat is considered as the more sensitive of the two species and will be evaluated for purposes of estimating a safe starting dose for a First in Human (FIH) study conducted in subjects with advanced malignancies. As described in the ICH guidance document: *S9 Nonclinical Evaluation for Anticancer Pharmaceuticals*, a safe human starting dose based on assessment of toxicity in rodent species is 1/10 of the severely toxic dose in 10% of the animals (STD 10). The STD 10 for ARQ 087 was determined to be 50 mg/kg/day, however, due to the need to sacrifice the 50 mg/kg/day animals between Days 12 and 14 of the dosing phase (except those designated for recovery), the 15 mg/kg dose was used to select the safe starting dose in humans. From this dose, the Phase 1 starting dose is calculated to be 9 mg/m^2/day or 15.3 mg/day (BSA 1.7). For the purpose of this FIH study the starting dose is suggested to be 25 mg every other day (QOD) to conform to available capsule dosage strengths (25 and 100 mg) and minimize capsule consumption burden for subjects.

### 4.4 Criteria for Dose Escalation and Determination of Dose-Limiting Toxicity

Evaluable subjects are defined as having been exposed to at least 28 days of continuous administration of ARQ 087 (e.g., qod, qd, 2 weeks on/1 week off, etc.). Based on the tolerability and safety of ARQ 087 evaluable subjects, enrollment at the next dose level and/or additional subjects into the ongoing cohort will occur according to the following:

- If zero of three initially treated subjects experience a DLT by Day 29 of continuous dosing, then dose escalation will occur
- If one of three initially treated subjects experiences a DLT by Day 29 of continuous dosing, then an additional three subjects will be enrolled for a total of six subjects treated

at the same dose level. Escalation will occur if no additional DLTs are seen in that cohort.

- If two or more of three initially treated subjects at a dose level experience a DLT by Day 29 of continuous dosing, dose escalation will stop and the prior dose level will be considered the MTD. If the first dose results in MTD, subsequent subjects will be enrolled at a lower dose or at a less frequent drug administration schedule (e.g., 25 mg/twice a week).

The MTD is defined as the dose level at which no more than one out of six subjects has an observable DLT.

Preliminary PK results reported in subjects enrolled in Cohorts 1-10 and the Food-effect Cohort have shown that ARQ 087 has a long half-life (~ 1 week) and accumulates (~4 to 14 fold across all cohorts, 4 to 8 fold in cohorts dosed at  $\geq 100$  mg qd) with continuous dosing. To determine MTD or RP2D and drug administration schedules, clinical PK parameters will be continuously monitored and assessed throughout the study.

Based on the drug safety profile and preliminary Food-effect Cohort PK data, 300 mg qd under fasting conditions has been defined as the RP2D and is recommended for further evaluation in the Expanded Cohort.

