### **Cohort 5 and all Subsequent Dose Escalation/Food-effect Cohorts (Part 1)**

Tumor assessments (CT scan, MRI, or PET scan) will be performed at Baseline, and every eight weeks during Treatment Period 2 (e.g., on Day 1 of every odd cycle, Cycle 3 Day 1, Cycle 5 Day 1, or Week 8, Week 16, etc.) or as otherwise clinically indicated.

Dose escalation will be performed after three or six subjects are evaluated in each cohort (see Table 4.1). If a DLT is observed in one of the three subjects in a cohort in the first 28 days of therapy, the additional three subjects will be enrolled in the cohort sequentially.

If no DLT is seen in the first three evaluable subjects in the first 28 days of therapy, dose escalation will occur and another three subjects will be enrolled and treated at the next ARQ 087 dose level. If two or more subjects experience a DLT at Dose Level 1, subsequent subjects will be enrolled at a lower dose or at a less frequent drug administration schedule (e.g., 25 mg twice a week). If a subject withdraws from study treatment for any reason other than a DLT during the first 28 days (first cycle), that subject will be replaced.

The MTD is defined as the dose level at which no more than one subject with a DLT is observed among six subjects. Once the MTD is determined, up to six additional subjects may be treated at this dose level of ARQ 087. If the MTD is not reached, dose escalation will proceed with the purpose of determining a RP2D of ARQ 087.

In the first four cohorts, the dose may be doubled, and in the next cohorts, the dose escalation will follow a modified Fibonacci scheme (increase by 50%, 30%, and 25%) until RP2D or MTD is determined.

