#### 4.5 Dose-Limiting Toxicity

Dose-limiting toxicities will be determined during the first four weeks/28 days (first cycle) of Treatment Period 2 (Cohorts 1-4) or during Cycle 1 (Cohort 5 and all subsequent cohorts). A DLT is defined by the occurrence of any of the following toxicities related to ARQ 087 within the first 28 days of continuous treatment (Treatment Period 2 or Cycle 1 of Continuous Dosing) and graded according to the Common Terminology Criteria for Adverse Events (CTCAE) version 4.03:

- Grade 4 anemia
- Grade 4 neutropenia
- Grade 4 thrombocytopenia
- Grade 3 neutropenia with fever ( $\geq 38^{\circ}\text{C}/100.4^{\circ}\text{F}$ )
- Grade 3 neutropenia lasting longer than 7 days despite optimal treatment
- Grade 3 thrombocytopenia in the presence of bleeding
- $\geq$  Grade 3 hyperglycemia (fasting blood glucose  $> 250$  mg/dL or non-fasting  $> 500$  mg/dL) requiring insulin (uncontrolled with metformin)
- $\geq$  Grade 3 non-hematological toxicity of any duration, except for the following:
  - Nausea, vomiting, or diarrhea responding to optimal medical management within 48 hours
  - Alopecia
- Any other toxicity that in the view of the Investigator represents a clinically significant hazard to the subject

**Note:** During the dose escalation phase, if the subject experienced a DLT, such subject should be permanently discontinued from the treatment.

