## 7.4 Treatment Compliance

A subject is considered compliant with the study protocol when study medication is administered at a compliance level of  $\geq 80\%$ . In order to evaluate the safety of ARQ 087, replacement of non-compliant subjects will be allowed during Cycle 1 of Treatment Period 2/Continuous Dosing.

Compliance will be calculated using the following equation:

(Number of capsules actually ingested / number of capsules that should have been ingested per dose level) x 100 = % compliance

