5.4.6 Exposure Analyses

Dosing and Extent of Exposure

Duration of exposure is defined as the total number of days on the study drug. The following algorithm will be used to calculate the duration of study treatment exposure for subjects who took at least one dose of ARQ 087:

Duration of exposure (days) = [(date of last administration of study treatment) – (date of first administration of study treatment) + 1]

Temporary drug discontinuation will be ignored. If the date of the last administration is unknown, the date until which the dispensed drug should last without counting any extra drug provided will be used.

Treatment Compliance

A subject is considered compliant with the study protocol when study medication is administered at a compliance level of $\geq 80\%$. In order to evaluate safety of ARQ 087, replacement of non-compliant subjects will be allowed during the first 28 days of dosing.

Compliance will be calculated using the following equation:

$\% \text{ compliance} = (\text{Number of capsules actually ingested} / \text{number of capsules that should have been ingested per dose level}) \times 100$

This treatment compliance will be summarized for safety population per treatment groups and overall.

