5.4.7 Analyses of Safety Variables

All analyses for the safety variables will be performed on safety population. Safety variables include adverse events, laboratory parameters, vital signs, ECOG performance status, 12-lead ECG and physical exams.

Descriptive statistics will be calculated for quantitative safety data, frequency counts and percentages will be compiled for classification of qualitative safety data. All percentages will be calculated based on the number of subjects in the safety population, unless otherwise indicated. Baseline is defined as the last non-missing value prior to the first dose date or on day 1, unless otherwise noted.

Adverse Events

Adverse events will be evaluated for severity using NCI-CTCAE, version 4.03. AE summaries will include treatment-emergent adverse events (TEAEs).

A TEAE is defined as:

- an AE which is not present prior to the first dose of ARQ 087 and started after taking the study drug during the treatment period or within 30 days after the last dose of the study drug;
- an AE which is present prior to the first dose of ARQ 087 and increased in severity after taking study drug during the treatment period or within 30 days after the last dose of study drug;
- an AE which is considered study drug-related regardless of the start date of the event.

All TEAEs will be coded using Medical Dictionary for Regulatory Activities (MedDRA[®]) Version 15.1 and summaries will be presented by system organ class and preferred term. Separate TEAE summaries will be generated for the following categories:

- All TEAEs
- Severe TEAEs (Grade 3 or higher)
- SAEs
- TEAEs related to study drug
- TEAEs leading to treatment discontinuation
- TEAEs leading to treatment interruption
- TEAEs leading to treatment interruption then dose reduction
- TEAEs resulting in death
- TEAEs listed according to maximum severity
- TEAEs classified as DLTs

TEAEs will be summarized by presenting the number and percentage of subjects having at least one TEAE in each system organ class and preferred term. A subject with multiple occurrences of the same TEAE will be counted only once in the AE category.

Separate TEAE summaries will be presented by system organ class, preferred term, and maximum CTCAE 4.03 grade. A subject with multiple CTCAE grades for the same TEAE will be summarized under the maximum CTCAE grade recorded for the event.

Laboratory Test

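### Protocol 4.4 defines evaluable subjects in a way that leaves out those who stop early for a DLT, and the SAP has no DLT population, so its DLT table is divided by everyone treated

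*Protocol*

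**What the plan says.** **Evaluability.** Protocol 4.4 states: "Evaluable subjects are defined as having been exposed to at least 28 days of continuous administration of ARQ 087". The next sentence ties decisions to that set: "Based on the tolerability and safety of ARQ 087 evaluable subjects, enrollment at the next dose level". Section 4.1.1 does the same: "If no DLT is seen in the first three evaluable subjects in the first 28 days of therapy, dose escalation will occur".

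**Stopping after a DLT.** Protocol 4.5: "During the dose escalation phase, if the subject experienced a DLT, such subject should be permanently discontinued from the treatment". The synopsis and section 7.3 say the same.

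**Counting unit in the escalation bullets.** Section 4.4 switches from evaluable to treated subjects: "If zero of three initially treated subjects experience a DLT by Day 29 of continuous dosing, then dose escalation will occur". The synopsis bullets also count treated subjects.

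**Replacement.** The synopsis and section 4.1.1 replace a subject who withdraws in the first cycle, unless the reason is a DLT. Protocol 7.4 adds that "replacement of non-compliant subjects will be allowed during Cycle 1 of Treatment Period 2/Continuous Dosing", with non-compliance meaning less than 80% of the capsules due. SAP 5.4.6 gives a different window: "replacement of non-compliant subjects will be allowed during the first 28 days of dosing".

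**Reporting.** SAP section 4 names four populations: enrolled, safety, pharmacokinetic and evaluable. The last is the response set (one cycle plus one post-baseline tumor evaluation). None is a DLT set. SAP 5.4.7 lists a table of TEAEs classed as DLTs and states: "All percentages will be calculated based on the number of subjects in the safety population, unless otherwise indicated". SAP 4.2 admits anyone who took any amount of drug. SAP 5.2 puts all cohorts in every summary table, by dose group and with an Overall column.

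**The concern.** Safety and tolerability is the primary objective, and finding the MTD or RP2D is a secondary one. The DLT count and its denominator are the main numbers behind both. A definition that admits only subjects with 28 days on drug, next to a rule that takes subjects with a DLT off drug, removes the events that the set exists to count.

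The reporting side has the opposite fault: its denominator is too wide. It holds subjects who were replaced because they were not considered to inform the DLT question. In the Overall column it also holds the Expanded Cohort, although the synopsis labels the DLT criteria as Part 1. A reader of the final table could not tell which rate is shown.

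**Working it through.** The documents state no operating characteristic or DLT rate, so there is no plan figure to reproduce. The check sets the passages side by side and adds small illustrations.

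**1. Who is counted?**

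| Place | Counting unit | Subject with an early Cycle 1 DLT |
|---|---|---|
| Protocol 4.4, definition | 28 days of administration | excluded as written |
| Protocol 4.1.1 | first three evaluable subjects | excluded if the 4.4 definition applies |
| Protocol 4.4 and synopsis, bullets | treated subjects | included |
| Synopsis and 4.1.1, replacement | withdrawals other than for a DLT are replaced | kept, not replaced |
| SAP 4.2 and 5.4.7, DLT table | anyone given any drug | included, along with replaced subjects |

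Take six treated subjects, two of whom stop early for a DLT. The bullets give 2/6 = 33.3%. The section 4.4 definition taken alone gives 0/4 = 0%. The second figure shows what the sentence says, not how the trial was likely run.

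**2. Dilution in the SAP table.** Take one DLT among six evaluable subjects, with two further subjects replaced. The DLT-evaluable rate is 1/6 = 16.7%. The safety-population rate is 1/(6 + 2) = 1/8 = 12.5%, which is 4.2 percentage points lower. The SAP tabulates by pooled dose group, so this shows the mechanism and does not predict a cell.

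For the Overall column, use the upper planning figures: 120 subjects in all, 60 of them in the Expanded Cohort, leaving 60 in Part 1. If DLTs are recorded only in Part 1, k DLTs are reported as k/120 instead of k/60, which is half the rate.

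**3. When does a hold make a subject replaceable?** Compliance = capsules taken / capsules due × 100, over 28 days:

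- Once daily, 5 of 28 doses missed: 23/28 = 82.1%, compliant.
- Once daily, 6 of 28 missed: 22/28 = 78.6%, replaceable.
- Every other day, 2 of 14 missed: 12/14 = 85.7%, compliant.
- Every other day, 3 of 14 missed: 11/14 = 78.6%, replaceable.
- Once daily, a 14-day hold (a length that Table 7.1 contemplates): 14/28 = 50%.

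These figures apply only if doses held on instruction count as due. Protocol 7.4 and SAP 5.4.6 do not say. The two windows also differ: in Cohorts 1–4 dosing begins with the single dose of Treatment Period 1, at least 72 hours before Cycle 1 Day 1.

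**4. Direction of the replacement effect.** Let a be the chance of a DLT and b the chance of toxicity short of a DLT that leads to replacement. Both are assumed, over 0.1 to 0.3. Among counted subjects the DLT rate becomes a/(1 − b). Under the 3+3 rule, with DLT rate p, P(escalate) = (1 − p)³ + 3p(1 − p)² × (1 − p)³.

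| a, b | Kept as non-DLT (p = a) | Replaced (p = a/(1 − b)) | Counted as DLT (p = a + b) |
|---|---|---|---|
| 0.1, 0.1 | 0.906 | 0.887 | 0.709 |
| 0.2, 0.2 | 0.709 | 0.600 | 0.309 |
| 0.3, 0.3 | 0.494 | 0.265 | 0.082 |

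For a = b = 0.2 the counted rate rises from 0.20 to 0.20/0.80 = 0.25. Replacement removes non-events, so it makes escalation less likely than keeping those subjects as non-DLTs. It makes escalation more likely only against a rule that would call them DLTs.

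**The case against.** The strongest reply is that the protocol's other text already gives the working rule. Only withdrawals for reasons other than a DLT are replaced, and the bullets that decide escalation count treated subjects. Nobody could run a 3+3 design in which DLTs do not count. This stands as an account of likely conduct. It does not repair section 4.4, which contains both counting units and states that decisions rest on evaluable subjects.

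A reader might go further and infer that subjects who stop or hold drug for toxicity fall out of the escalation count, biasing DLT rates toward zero. The documents do not support that:

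- Subjects with a protocol-defined DLT stay in the working count.
- Many Grade 3–4 toxicities that call for a hold under Table 7.1 are already DLTs in Cycle 1 under section 4.5. The remainder, such as Grade 3 thrombocytopenia without bleeding, may still be captured by the investigator-judgement criterion.
- Section 4.4 gives every-other-day and two-weeks-on, one-week-off dosing as examples of continuous administration, and the exposure definitions ignore temporary interruptions. A hold therefore does not clearly fail the 28-day test.
- Replacement for low compliance is permitted, not required.
- Replacing subjects without a DLT raises the counted rate, as step 4 of the working shows.

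Two further points are fair. An all-treated denominator is normal for adverse-event tables, and the DLT table does not set the MTD. The RP2D is also already fixed in both documents, so new wording cannot alter past escalation decisions. What remains is the reported DLT rate, which is still to be produced and has no stated population of its own.

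**Conclusion.** The point holds in a limited form. As written, the section 4.4 definition excludes subjects who stop early for a DLT, and it conflicts with the escalation bullets and the replacement rule. The SAP supplies no DLT-evaluable set, so its DLT percentages are computed on all treated subjects, including replaced ones, and the Overall column includes the Expanded Cohort.

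The illustrated size is 12.5% against 16.7% for two replacements alongside six evaluable subjects, and up to a halving in the Overall column at the upper planning figures. The first depends on an assumed number of replacements. The second depends on DLTs being a Part 1 outcome, as the synopsis labels them; section 4.5 itself refers to Cohort 5 and all later cohorts, so the SAP should say which applies.

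The passages on holds, compliance and replacement are unclear. No bias toward zero is claimed for that route, because its direction depends on the comparator.

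**What to change.** 1. In Protocol 4.4 and SAP section 4, define one DLT-evaluable set: subjects with a DLT in the first 28 days of continuous dosing, or who completed that window. Use the same term in section 4.1.1 and in the escalation bullets.
2. In SAP 5.4.7, name that set as the denominator of the DLT table, and state whether the Expanded Cohort belongs in the table and its Overall column.
3. List every replaced subject with cohort, reason for replacement and toxicities, so that those who left with toxicity short of a DLT remain visible.
4. Ask the sponsor to reconcile the synopsis and section 4.1.1 (replacement after withdrawal), Table 7.1 (toxicity holds), and Protocol 7.4 with SAP 5.4.6 (replacement below 80% compliance, with differing windows). The result should say whether doses held on instruction count as missed, and how interruptions bear on completing the window. Which clinical rule applies is for the sponsor to decide.

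The cost is wording in two documents, one re-derived table and one listing. DLT rates may look slightly higher than on the safety population. No dose or DLT criterion changes.
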